9.5.3 Appropriateness of Measurements

All clinical assessments are standard measurements commonly used in studies of relapsed or refractory solid tumors.

The safety assessments to be performed in this study, including hematology analyses, blood chemistry tests, urinalysis, radiologic studies, and assessment of AEs, are standard evaluations to ensure subject safety. The use of RECIST 1.1 for tumor assessments of solid tumors is widely accepted (see [Appendix 1](#)) ([Eisenhauer, et al., 2009](#)).

9.5.4 Reporting of Serious Adverse Events, Pregnancy, and Events Associated with Special Situations

9.5.4.1 Reporting of Serious Adverse Events

All SERIOUS ADVERSE EVENTS, regardless of their relationship to study treatment, must be reported on a completed SAE form by email or fax as soon as possible but no later than 24 hours from the time the investigator becomes aware of the event.

Deaths and life-threatening events should be reported immediately by telephone. The immediate report should be followed up within 24 hours by emailing or faxing the completed SAE form.

Serious adverse events, regardless of causality assessment, must be collected through the last visit and for 30 days after the subject's last dose, whichever occurs first. All SAEs must be followed to resolution or, if resolution is unlikely, to stabilization. Any SAE judged by the investigator to be related to the study treatment or any protocol-required procedure should be reported to the sponsor regardless of the length of time that has passed since study completion.

The detailed contact information for reporting of SAEs is provided in the Investigator Study File.

For urgent safety issues, please ensure all appropriate medical care is administered to the subject and contact the appropriate study team member listed in the Investigator File.

It is very important that the SAE report form be filled out as completely as possible at the time of the initial report. This includes the investigator's assessment of causality.

Any follow-up information received on SAEs should be forwarded within 24 hours of its receipt. If the follow-up information changes the investigator's assessment of causality, this should also be noted on the follow-up SAE form.

Preliminary SAE reports should be followed as soon as possible by detailed descriptions including copies of hospital case reports, autopsy reports, and other documents requested by the sponsor.

The investigator should notify his/her IRB/IEC of the occurrence of the SAE, in writing, in accordance with local requirements. A copy of this communication must be forwarded to the sponsor and/or the designated CRO monitor and filed in the Trial Master File.

9.5.4.2 Reporting of Pregnancy and Exposure to Study Drug Through Breastfeeding

Any pregnancy in which the estimated date of conception is either before the last visit or within 30 days of last study treatment, or any exposure to study drug through breastfeeding during study treatment or within 30 days of last study treatment, must be reported.

If an adverse outcome of a pregnancy is suspected to be related to study drug, this should be reported regardless of the length of time that has passed since the exposure to study treatment.

A congenital anomaly, death during perinatal period, an induced abortion, or a spontaneous abortion are considered to be an SAE and should be reported in the same time frame and in the same format as all other SAEs (see Reporting of Serious Adverse Events [Section 9.5.4.1]).

Pregnancies or exposure to study drug through breastfeeding must be reported by fax or email as soon as possible but no later than 24 hours from the time the investigator becomes aware of the pregnancy. The contact information for the reporting of pregnancies and exposure to study drug through breastfeeding is provided in the Investigator Study File. The Pregnancy Report Form must be used for reporting. All pregnancies must be followed to outcome. The outcome of the pregnancy must be reported as soon as possible but no later than 24 hours from the time the investigator becomes aware of the outcome.

A subject who becomes pregnant must be withdrawn from the study.

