9.1.3 Post-treatment (All Cohorts)

The Post-treatment Follow-up begins when the subject discontinues treatment. After subject discontinues treatment, an Off-Treatment Visit and the procedures noted in the Schedule of Assessments Tables ([Table 7](#), [Table 8](#), and [Table 9](#)) should be completed within 30 days after the last dose of drug. Subjects will be followed for survival every 3 months until death or for 1 year, whichever occurs first, unless the study is terminated or the subject discontinues due to withdrawal of consent or is lost to follow-up (see [Section 9.3.3](#)).

Subjects who discontinue treatment without disease progression will have tumor assessments performed every 6 or 8 weeks (per the appropriate tumor assessment schedule) for up to 1 year, or sooner if clinically indicated, for documented disease progression or until another anticancer therapy is initiated whichever occurs first. After data cutoff, tumor assessments may be performed as clinically indicated using the institutional guidelines, following the prevailing local standard of care.

As required by some regulatory agencies, the following estimates are provided:

- The study will begin in December 2014 and will end on or before December 2017.
- The maximum estimated period for the study is anticipated to be approximately 36 months. However, subjects will continue to receive study treatment as long as they demonstrate clinical benefit. Subjects benefiting from study treatment in the opinion of the investigator will continue to receive treatment until disease progression, intolerable toxicity, subject noncompliance with safety or efficacy assessments, initiation of another anticancer therapy, voluntary discontinuation by the subject at any time, or study termination by the sponsor, whichever occurs first.

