 - total abstinence (if it is their preferred and usual lifestyle)
 - an intrauterine device or intrauterine hormone-releasing system (IUS)
 - an oral contraceptive. Subject must be on a stable dose of the same oral contraceptive product for at least 28 days before dosing and throughout the study and for 6 months after study drug discontinuation.) .
 - have a vasectomized partner with confirmed azoospermia.
- Do not agree to use a highly effective method of contraception (as described above) throughout the entire study period and for 6 months after study drug discontinuation.

For sites outside of the EU, it is permissible that if a highly effective method of contraception is not appropriate or acceptable to the subject, then the subject must agree to use a medically acceptable method of contraception, ie, double-barrier methods of contraception such as condom plus diaphragm or cervical/vault cap with spermicide.

NOTE: All females will be considered to be of childbearing potential unless they are postmenopausal (amenorrheic for at least 12 consecutive months, in the appropriate age group, and without other known or suspected cause) or have been sterilized surgically (ie, bilateral tubal ligation, total hysterectomy, or bilateral oophorectomy, all with surgery at least 1 month before dosing).

Males who have not had a successful vasectomy (confirmed azoospermia) or they and their female partners do not meet the criteria above (ie, not of childbearing potential or practicing highly effective contraception throughout the study period and for 5 times the half-life of the study drug plus 90 days after study drug discontinuation). No sperm donation is allowed during the study period and for 5 times the half-life of the study drug plus 90 days after study drug discontinuation.

Males who have not had a successful vasectomy (confirmed azoospermia) or they and their female partners do not meet the criteria above (ie, not of childbearing potential or practicing highly effective contraception throughout the study period and for 6 months after study drug discontinuation). If the female partner is pregnant, then males who do not agree to use condoms throughout the study period and for 6 months after study drug discontinuation. No sperm donation is allowed during the study period and for 6 months after study drug discontinuation.

Cohort 3B (Combination Expansion): Osteosarcoma subjects who progressed in Cohorts 1 or 2B and opt to receive combination therapy:

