Progression of malignant disease under study should not be recorded as an AE in studies where it is included as an endpoint for underlying disease. Signs and symptoms clearly related to the progression of disease should not be captured as an AE. If the progression leads to an untoward medical occurrence, then this medical occurrence should be recorded as an AE.

All AEs, regardless of relationship to study drug or procedure, should be collected beginning from the time the subject signs the study consent through the last visit and for 30 days following study drug discontinuation.

All AEs must be followed for 30 days after the subject's last dose, or until resolution, whichever comes first. All SAEs must be followed to resolution or, if resolution is unlikely, to stabilization.

Every effort must be made by the investigator to categorize each AE according to its severity and its relationship to the study treatment.

Assessing Severity of Adverse Events

Adverse events will be graded according to Common Terminology Criteria for Adverse Event (CTCAE v4.03) ([Appendix 2](#)).

Investigators will report CTCAE grades for all AEs (for both increasing and decreasing severity). All adverse events reported using CTCAE classification and graded as 4 or 5 are to be considered serious. Adverse events that are not reported in the CTCAE will be graded on a 4-point scale (mild, moderate, severe, and life-threatening).

Assessing Relationship to Study Treatment

Items to be considered when assessing the relationship of an AE to the study treatment are:

- Temporal relationship of the onset of the event to the initiation of the study treatment
- The course of the event, especially the effect of discontinuation of study treatment or reintroduction of study treatment, as applicable
- Whether the event is known to be associated with the study treatment or with other similar treatments

- The presence of risk factors in the study subject known to increase the occurrence of the event
- The presence of nonstudy, treatment-related factors that are known to be associated with the occurrence of the event

Classification of Causality

Not Related: A causal relationship between the study treatment and the AE is not a reasonable possibility

Related: A causal relationship between the study treatment and the AE is a reasonable possibility. The investigator must further qualify the degree of certainty as “possible” or “probable.”

Serious Adverse Events and Other Events of Interest

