- u. Survival data will be collected every 3 months until death or 1 year as per the protocol. All anticancer therapies will be collected.
- v. Concomitant medications will be recorded throughout the study and for 30 days after last dose. All anticancer therapy will be recorded until time of death or termination of survival follow-up.
- w. AEs will be recorded from the date of signed informed consent, throughout the study, and for 30 days after the last dose. SAEs irrespective of relationship to study treatment must be reported as soon as possible but not later than 24 hours. A diary will be provided to the subject to capture any abnormal gastrointestinal symptoms (eg, diarrhea, abdominal discomfort, cramps) experienced during the study.

Table 8 Schedule of Assessments – Cohort 2A – Differentiated Thyroid Cancer and Cohort 2B - Osteosarcoma

Phase	Pretreatment		Treatment ^a (All cycles are 28 days in duration)																			Post-Treatment		
	Screening ^b	Baseline ^c	Treatment ^d																		Off-Tx	Follow-up ^e		
Visit	1	2	3	4	5	6	7	8	9	10	11	12	13	14	15	16	17	18	19	20	99			
Cycle			Cycle 1					Cycle 2					Cycle 3					Cycle 4					Cycle 5-Last	
Day	-28 to -2	-1	1	8	15	22	1	8	15	22	1	8	15	22	1	8	15	22	1	15				
Procedures/Assessments																								
Informed consent	X																							
Inclusion/exclusion	X	X																						
Demographic data	X																							
Medical/surgical history	X	X																						
Prior medication/ procedures	X	X																						
Pregnancy test ^f	X	X																					X	
Lansky play score/ Karnofsky PS ^g	X	X					X				X				X			X			X			
TNM Staging	X																							
Physical examination ^h	X	X			X		X				X				X			X			X		X	
Vital signs ⁱ	X	X	X		X		X		X		X		X		X		X	X		X	X	X		
12-lead ECG ^j	X					X				X			X			X			X			X		
Echocardiogram ^k	X		Performed every 16 weeks following the first dose of study drug or sooner, if clinically indicated																		X			
Clinical chemistry and hematology ^l	X	X		X		X		X		X		X		X		X		X		X		X		
Guaiac Fecal occult blood test ^l	X	X				X				X			X			X				X		X		
Urine dipstick testing ^m	X	X		X	X	X	X	X	X	X	X	X	X	X	X	X	X	X	X	X	X	X		
PK blood samples ⁿ			X		X		X																	
Study treatment			Once Daily (lenvatinib) [based on BSA calculations at Day 1 of each Cycle]																					
Palatability Questionnaire			X																					

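### The pregnancy-reporting window has a fixed limit of only 30 days after treatment and otherwise an undefined last visit, while the contraception requirement runs to 6 months

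*Protocol*

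**What the plan says.** **Reporting window.** Protocol 9.5.4.2 requires a report of any pregnancy with an estimated conception date "either before the last visit or within 30 days of last study treatment". Once reported, "All pregnancies must be followed to outcome". An adverse pregnancy outcome suspected to be drug-related is reportable "regardless of the length of time that has passed since the exposure to study treatment".

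**Contraception period.** Exclusion criterion 14 (Protocol 9.3.2, repeated in the synopsis) excludes females of childbearing potential who do not agree to highly effective contraception "throughout the entire study period and for 6 months after study drug discontinuation". For males there are two consecutive paragraphs. One sets 5 times the half-life of study drug plus 90 days. The next sets 6 months and ends: "No sperm donation is allowed during the study period and for 6 months after study drug discontinuation".

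**Visits after treatment.** Section 9.1.3 places the Off-Treatment Visit first; it and its procedures "should be completed within 30 days after the last dose of drug". Survival is then followed every 3 months for up to 1 year. Height is measured every 3 months over the same year (section 9.5.1.5). Tumor scans continue for up to 1 year in subjects who stopped without progression. The last scheduled pregnancy test is at the Off-Treatment Visit.

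**The concern.** The sponsor's own eligibility rule treats the 6 months after study drug as a period in which conception should be avoided. A pregnancy conceived in that period is therefore one the sponsor would want to hear about. The only fixed limit on reporting is 30 days. Whether the window reaches further depends on what a site takes the last visit to be.

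What could be missed are uneventful pregnancies, and outcomes that nobody attributes to study drug, in a study that enrols adolescents and, for osteosarcoma, adults up to age 25. Capture could differ from site to site. Section 9.5.4.2 refers to any pregnancy but does not name partners of male subjects, so that coverage is also left to interpretation.

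**Working it through.** The plan has no figure of its own to reproduce. The check sets the windows side by side.

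**Inputs**
- Contraception term: 6 months (criterion 14). Shorter male term: 5 half-lives plus 90 days.
- Lenvatinib terminal half-life: about 28 to 30 hours (Protocol 7.1.3.2). The protocol gives no half-life for ifosfamide or etoposide, so the shorter term is converted to days for lenvatinib only.
- Month length: 30.4375 days (SAP 8.3.2).
- Fixed reporting limit: 30 days after last treatment (Protocol 9.5.4.2).
- Day of last visit, *V*: not defined, so treated as an assumption and varied.

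**Terms in days**
- 6 × 30.4375 = 182.6 days.
- 5 × 28 h = 140 h = 5.8 days, and 5 × 30 h = 150 h = 6.25 days. Adding 90 gives about 96 days.

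**Uncovered time.** The two limbs are joined by *or*, so conception is covered up to the later of day 30 and *V*. For a contraception term *T*, gap = max(0, *T* − max(30, *V*)).

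| Reading of last visit | Covered to day | Gap, 6-month term | Gap, shorter male term |
|---|---|---|---|
| Off-Treatment Visit (by day 30), or no later visit takes place | 30 | 182.6 − 30 = 152.6 (83.6%) | 96 − 30 = 66 |
| Follow-up visits count, last one at month 3 | 3 × 30.4375 = 91.3 | 182.6 − 91.3 = 91.3 (50%) | 96 − 91.3 = about 5 |
| Follow-up visits count and reach month 6 or later | 182.6 or more | 0 | 0 |

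**Text for the shorter reading.** Section 9.5.1.5 collects adverse events "through the last visit and for 30 days following study drug discontinuation", which pairs the same term with 30 days. The adverse-event footnote to Table 7 records them "throughout the study, and for 30 days after the last dose". Section 9.5.4.1 ends routine SAE collection at the earlier of the last visit and 30 days.

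**Text for the longer reading.** Height and scans in follow-up require attendance. Tables 7 to 9 have a post-treatment follow-up column. Section 9.3.3 speaks of off-treatment study visits in the plural.

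**How secure the longer reading is.** Section 9.3.3 lets the sponsor halt survival follow-up after the primary analysis. Section 5.1 ends the study at the final data cutoff or the last subject's last treatment, whichever is later. Neither says whether follow-up visits continue for subjects treated late.

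**The case against.** **No rule is broken.** Nothing in the documents says the reporting window must equal the contraception period. One is a precautionary eligibility rule and the other a collection rule, and 30 days matches the adverse-event windows. This stands: the point is an improvement, not a breach.

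**The wording may already cover the period.** The limbs are alternatives, without the whichever-is-first limit used for SAEs. If the last visit were the Off-Treatment Visit, the first limb would add nothing after day 30. The adverse-event sections do not define the term. This also stands, and it is why zero is one end of the range. It shows the longer reading is available, not that every site will adopt it.

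**Halted follow-up is inference.** Section 9.3.3 mentions only survival follow-up, and section 5.1 defines study end for notifying authorities. Agreed: neither shows that visits stop, only that the protocol does not settle it.

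**Backstops exist.** Suspected drug-related adverse outcomes and related SAEs have no time limit. Section 9.5.1.5 lists pregnancy as an event of interest and counts a congenital anomaly in an exposed subject's child as an SAE, whatever the subject's sex. Section 9.5.4.2 also classes perinatal death and induced or spontaneous abortion as SAEs. These narrow the harm. They do not set a conception window, and the two unlimited routes need someone to learn of the event and suspect the drug.

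**Other papers may fill the gap.** The pregnancy report form and the investigator file are not available, and consent pages were removed before review. A reader might infer that partner coverage or self-report instructions are missing from the study. The documents do not support that, and no consent wording is proposed here.

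**Conclusion.** The point holds as a minor inconsistency between two windows in the same protocol. Its size is conditional: from 0 to about 153 of 183 days, or 0 to about 66 of 96 days on the shorter male term. Everything turns on the assumed day of the last visit. The documents give no expected number of pregnancies, so the range measures uncovered time and not missed cases.

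Two stronger readings are tempting. The first is that five months of the contraception period go unmonitored in every subject. The documents do not support this, because a subject seen at month 6 or later has no gap if follow-up visits count. The second is that drug-related harm to a child would escape reporting. That is not supported either, because suspected drug-related outcomes and related SAEs are reportable at any time.

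The 6-month term is used for both sexes because both male paragraphs stand as exclusion criteria and a male subject must satisfy the longer one. That the shorter paragraph is a leftover is a reasonable inference; the protocol does not say so. No sample size, endpoint or analysis is touched.

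**What to change.** 1. Amend section 9.5.4.2 to require reporting, and follow-up to outcome, of any pregnancy in a subject, or in a male subject's partner with her agreement, conceived during treatment or within 6 months after the last dose of any study drug (lenvatinib, ifosfamide or etoposide). The rule then no longer depends on the meaning of last visit.
2. Ask about pregnancy at the 3-monthly follow-up contacts already scheduled for 1 year.
3. Delete the male paragraph giving 5 half-lives plus 90 days from criterion 14 in the synopsis and section 9.3.2, so that one 6-month period applies to both sexes.

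The cost is amended protocol wording, one question at existing contacts, and some partner follow-up that depends on the partner's agreement. No visit is added. A subject whose follow-up has been halted would not be asked, but the reporting duty would still apply if the investigator learned of the pregnancy.

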9.5.4.3 Reporting of Events Associated with Special Situations

REPORTING OF ADVERSE EVENTS ASSOCIATED WITH STUDY DRUG OVERDOSE, MISUSE, ABUSE, OR MEDICATION ERROR

Adverse events associated with study drug overdose, misuse, abuse, and medication error refer to AEs associated with uses of the study drug outside of that specified by the protocol. Overdose, misuse, abuse, and medication error are defined as follows:

Overdose	Accidental or intentional use of the study drug in an amount higher than the protocol-defined dose
Misuse	Intentional and inappropriate use of study drug not in accordance with the protocol
Abuse	Sporadic or persistent intentional excessive use of study drug accompanied by harmful physical or psychological effects

Medication error Any unintentional event that causes or leads to inappropriate study drug use or subject harm while the study drug is in the control of site personnel or the subject.

All AEs associated with overdose, misuse, abuse, or medication error should be captured on the Adverse Event CRF and also reported using the procedures detailed in Reporting of Serious Adverse Events ([Section 9.5.4.1](#)) even if the AEs do not meet serious criteria. Abuse is always to be captured as an AE. If the AE associated with an overdose, misuse, abuse, or medication error does not meet serious criteria, it must still be reported using the SAE form and in an expedited manner but should be noted as nonserious on the SAE form and the Adverse Event CRF.

REPORTING OF SIGNIFICANT LABORATORY ABNORMALITY

Any significant treatment-emergent laboratory abnormality that meets the criteria described below and is observed during the clinical study should be entered on the Adverse Event CRF and reported using the procedures detailed in Reporting of Serious Adverse Events ([Section 9.5.4.1](#)), even if the laboratory abnormality does not meet serious criteria. If the significant laboratory abnormality does not meet serious criteria, it must still be reported using the SAE form and in an expedited manner but should be noted as nonserious on the SAE form and the Adverse Event CRF.

A laboratory result should be considered a treatment-emergent significant abnormality if the result:

- Is within normal limits at baseline and has increased in severity to meet the sponsor's grading criteria for laboratory values of Grade 3 or above
- Is outside normal limits at baseline and increases in severity to the sponsor's grading criteria for laboratory values of Grade 4 or above. These abnormalities are automatically considered to be serious, with the exception of expected and reproducible hematologic abnormalities.
- Is otherwise considered by the investigator to meet serious criteria as defined in [Section 9.5.1.5](#)

Significant laboratory abnormalities should not be listed as separate AEs or SAEs if they are considered to be part of the clinical syndrome that is being reported as an AE or SAE.

REPORTING OF STUDY-SPECIFIC EVENTS

Study-specific events should be entered on the Adverse Event CRF and reported using the procedures detailed in Reporting of Serious Adverse Events ([Section 9.5.4.1](#)), even if the study-specific event does not meet serious criteria. If the event does not meet serious criteria, it must still be reported using the SAE form and in an expedited manner but should be noted as nonserious on the SAE form and the Adverse Event CRF.

